### **11.3.2 Statistical Methods**

The baseline value for clinical laboratory tests will be the last non-missing measurement on or before the day of the first dose of study drug. Values on Day 1 must also be before the time of first dose if time is available. The same baseline value will be used for all summaries of the data from the Treatment and Post-Treatment Period visits.

Changes from baseline to each post-baseline visit, including applicable post-treatment visits, will be summarized. Each protocol-specified laboratory parameter will be summarized with the sample size; baseline mean; visit mean; and change from baseline mean, standard deviation, minimum, median, and maximum.

Plots of mean change ( $\pm$  standard error) from baseline to each visit will be presented for ALT and bilirubin (total, direct, and indirect).

Hematology and chemistry data values will be categorized as low, normal, or high based on the normal ranges of the laboratory used for each sample. Shift tables from baseline to minimum value and from baseline to maximum value during treatment (Study Drug End Day  $\leq 2$ ) will be created. The shift tables will cross-tabulate the frequency of subjects with baseline values below/within/above the normal range versus minimum/maximum post-baseline values below/within/above the normal range.

The laboratory parameters listed in Table 11 will be categorized according to the toxicity grades defined in the table. The number and percentage of subjects with a maximum toxicity grade of 1, 2, 3 or 4 during treatment will be calculated. To be counted, the post-baseline value must have a toxicity grade that is more extreme than the toxicity grade corresponding to the baseline value. For each laboratory parameter in Table 11, the summary will also include the number and percentage of subjects with a maximum of at least Grade 3. These summaries will also be presented for the set of HCV/HIV co-infected subjects (determined at Screening) within the populations/groups specified in Section 11.1. A listing of all relevant laboratory parameters will be provided for each subject who had an increase to Grade 2 or higher for any laboratory variable in Table 11.

For the assessments of hepatotoxicity based on single and multiple laboratory parameters, the number and percentage of subjects meeting the criterion during treatment will be calculated for each criterion. A listing of all ALT, AST, total, indirect and direct bilirubin, ratio of direct to total bilirubin, and alkaline phosphatase values will be provided for each subject who met any of the single or multiple criteria defined above. The listings will be reviewed to assess bilirubin (e.g., mixed or direct predominance) and temporal relationships for subjects with ALT  $> 3 \times$  ULN (or ALT Grade 2+) and total bilirubin  $\geq 2 \times$  ULN.

## **11.4 Analysis of Vital Signs and Weight**

### **11.4.1 Variables and Criteria Defining Abnormality**

Vital sign variables are body temperature, sitting systolic blood pressure, sitting diastolic blood pressure, sitting pulse rate, and body weight.

The criteria for potentially clinically significant (PCS) vital sign findings are presented in Table 12.

**Table 12. Criteria for Potentially Clinically Significant Vital Sign Values**

Test/Measurement	Very Low (VL)	Very High (VH)
Systolic Blood Pressure	$\leq 90$ mmHg AND A decrease of $\geq 20$ mmHg from baseline	$\geq 180$ mmHg AND An increase of $\geq 20$ mmHg from baseline
Diastolic Blood Pressure	$\leq 50$ mmHg AND A decrease of $\geq 15$ mmHg from baseline	$\geq 105$ mmHg AND An increase of $\geq 15$ mmHg from baseline
Pulse Rate	$\leq 50$ bpm AND A decrease of $\geq 15$ bpm from baseline	$\geq 120$ bpm AND An increase of $\geq 15$ bpm from baseline
Weight	A decrease of $\geq 15\%$ from baseline	An increase of $\geq 15\%$ from baseline
Body Temperature		$> 38.3^{\circ}\text{C}$ AND An increase of $\geq 1.1^{\circ}\text{C}$ from baseline

#### 11.4.2 Statistical Methods

The baseline value for vital signs will be the last measurement on or before the day of the first dose of study drug. The same baseline value will be used for all summaries of the data from the Treatment and Post-Treatment Period visits.

Changes from baseline to each post-baseline visit, including applicable post treatment visits, will be summarized. Each vital sign parameter will be summarized with the baseline mean; visit mean; and change from baseline mean, standard deviation, minimum, median, and maximum.

The number and percentage of subjects with on-treatment values meeting the specified criteria for PCS vital sign values (Table 12) will be calculated. A post-baseline value must be more extreme than the baseline value to be considered a PCS finding. A separate listing will be provided that presents all vital sign values for the subjects meeting PCS criteria during treatment.

## **11.5 Analysis of Child-Pugh Score**

Child-Pugh scores will be categorized as 5, 6, > 6, or missing at baseline and each protocol-specified post-baseline visit, including applicable post-treatment visits. Shift tables from baseline to each post-baseline visit will be created. The shift tables will cross-tabulate the frequency of subjects with baseline values in each category versus the post-baseline categories. For each baseline category and across the baseline categories, the percentage of subjects in each post-baseline category (excluding the post-baseline category of missing) will be calculated.

## **11.6 Analysis of HIV-1 RNA and Flow Cytometry Data**

Plasma HIV-1 RNA will be measured by the central laboratory using the Roche COBAS AmpliPrep/COBAS TaqMan HIV-1 Test, version 2.0. For specimens with HIV-1 RNA results that are detectable but not quantifiable, the results are reported as "< 20 CP/ML HIV-1 RNA DETECTED;" for specimens with no HIV RNA detected, the results are reported as "NO HIV-1 RNA DETECTED." Subjects will also have blood samples drawn and archived. These samples may be used for other analyses including drug resistance testing. These samples may be tested at the discretion of AbbVie.

For the HCV/HIV co-infected subjects (determined at Screening) who are on HIV-1 ART at initiation of study drug, the number and percentage of subjects with 2 consecutive HIV-1 RNA values  $\geq 200$  copies/mL during the Treatment Period will be calculated; only data from the central laboratory will be included in this analysis. A listing of subjects with a plasma HIV-1 RNA value  $\geq 200$  copies/mL at any baseline or post-baseline visit during the study will be provided.

For the HCV/HIV co-infected subjects (determined at Screening), changes from baseline to each post-baseline visit, including applicable post-treatment visits, in CD4+ T-cell count (absolute and percentage), CD8+ T-cell count (absolute and percentage), and lymphocytes (count) will be summarized. Each parameter will be summarized with the sample size; baseline mean; visit mean; and change from baseline mean, standard deviation, minimum, median, and maximum.

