5.4.1.2 Failure to Maintain HIV Virologic Suppression

HIV-1 RNA will be assessed at each scheduled study visit during the Treatment Period and Post-Treatment Period, as detailed in [Appendix C](#).

For HCV/HIV-1 Co-Infected Subjects on Stable ART

The criteria for failure to maintain HIV virologic suppression is as follows:

- HIV-1 RNA ≥ 200 copies/mL confirmed on 2 consecutive tests at least 2 weeks apart, in a subject compliant with their HIV ART therapy.

At the time a confirmatory HIV-1 RNA is drawn, a sample for HIV-1 genotypic resistance testing may also be obtained; this sample may be analyzed if the subject's repeat plasma HIV-1 RNA is ≥ 500 copies/mL. A subject should remain on HCV study drug treatment and his/her current ART regimen while the failure to maintain HIV virologic suppression is being confirmed. A confirmatory HIV-1 RNA and HIV-1 genotypic resistance blood draw can be done as an unscheduled visit. However, if this blood draw falls on the date of a scheduled study visit ([Appendix C](#)), only a single HIV-1 RNA and HIV-1 genotypic resistance blood draw needs to be performed at this visit.

Clinical management of failure to maintain HIV-1 virologic suppression during the study (Treatment Period and Post-Treatment Period) will be handled by the site investigator according to current HIV treatment guidelines and local standard of care.

If the investigator wishes to change the HIV-1 ART regimen for a subject, it must be discussed with the AbbVie TA MD prior to the change being made, unless the change is being made to address an immediate safety concern.

During the Treatment Period, subjects with confirmed failure to maintain HIV-1 RNA suppression should continue study drug treatment unless there is a requirement for prohibited concomitant medications (Section 5.2.3.2 and Section 5.2.3.4) to construct a new HIV ART regimen.

For HCV/HIV-1 Co-Infected Subjects Naïve to ART

Clinical management of ART-naïve co-infected subjects during the study (Treatment Period and Post-Treatment period) will be handled by the site investigator according to current HIV treatment guidelines and local standard of care. During the Treatment Period, if an investigator deems it necessary to initiate HIV-1 ART for a subject, continuation of study drug treatment must be discussed with the AbbVie TA MD prior to ART initiation.

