8.1.5.3 HIV-1 RNA Data

For the HCV/HIV co-infected subjects who were on stable HIV-1 ART at initiation of study drug, the number and percentage of subjects with 2 consecutive HIV-1 RNA values ≥ 200 copies/mL during the Treatment Period will be calculated.

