- A complete medical history will be taken at Screening and will be updated at the Screening Visit.
- Height will be measured at the Screening Visit only. Waist circumference will be measured at the Screening Visit, but if it is not measured at Screening, it may be measured on Day 1.
- Only at Screening, for female subjects to assess postmenopausal state.

- g. Pregnancy testing is not required for females of non-childbearing potential as defined in Inclusion Criterion 3.
- h. Perform the test for HBV DNA if HBsAg is negative.
- i. For those with history of diabetes mellitus.
- j. For subjects who have not had a qualifying liver biopsy within the previous 24 months or a qualifying FibroScan[®] within the previous 6 months.
- k. If the sample is not collected at Study Day 1, it may be collected at any other visit during the study.
- l. See specific information regarding adverse event collection in Section 6.1.4.
- m. PROs should be administered before any study procedures. EOT PROs are at Week 12 EOT or Week 16 EOT, as applicable.
- n. Applicable only to those subjects enrolled into a 16-week treatment.
- o. Subjects should bring all the study drug to the study drug accountability visits at Weeks 4, 8, 12, EOT or Premature D/C. The site will record the number of tablets returned only at these visits.
- p. HCV/HIV co-infected subjects only.
- q. For HCV/HIV co-infected subjects on stable ART: As detailed in Section 5.4.1.2, a repeat HIV-1 RNA blood draw to confirm a HIV-a RNA result of ≥ 200 copies/mL can be done as an unscheduled visit, but must be performed at least 2 weeks apart from the prior HIV-1 RNA result. At the time the repeat plasma HIV-1 RNA is drawn, a sample may be obtained for HIV-1 resistance testing. If the confirmatory HIV-1 RNA lab draw falls on the date of a scheduled study visit, only a single HIV-1 RNA and HIV-1 resistance blood draw is needed at the visit.
- r. Details regarding timing of PK samples are provided in Section 5.3.2.1.
- s. For subjects participating in Optional Intensive PK sampling, additional PK samples will be drawn on Study Day 1 at 2, 4 and 6 hours post-dose and on Week 4 visit immediately prior to dose (0 hour) and 2 and 4 hours post-dose during the visit.

Study Activities – Post Treatment Period

Activity	PT Week 4	PT Week 12	PT Week 24 or PT D/C ^a
Vital Signs and Weight	X	X	X
Hematology/Chemistry/Urinalysis/Coagulation Panel	X		X ^b
Pregnancy Test (urine) ^c	X (u)		X (u) ^b

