**Table 4. Analysis Time Windows for HIV-1 RNA and Flow Cytometry Measurements (Treatment Period)**

Scheduled Visit	Nominal Day (Study Day)	Time Window (Study Day Range)
Day 1/Baseline a	1 a	≤ 1 a
Week 2	14	2 to 21
Week 4	28	22 to 42
Week 8	56	43 to 70
Week 12	84	71 to 98
Week 16 b	112	99 to 126
Final Treatment Visit c	2 to ≤ 2 days after last dose of study drug	

- a. Day of first dose of study drug.  
 b. For 16-week treatment only.  
 c. The last value within the window will be used to define the Final Treatment Visit value. The upper bound of this Final window is Study Drug End Day 2. Study Drug End Day 0 is defined as the day of the last dose of study drug.

Note: Time windows specified in this table are for HCV/HIV co-infected subjects only. For all windows, data must be on or before Study Drug End Day 2. The result closest to the scheduled time point will be used. Flow cytometry samples are collected at Day 1, Week 4, Week 12, and End of Treatment Visit.

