### **Definitions for Efficacy Endpoints**

A confirmed quantifiable value during treatment is defined as any two consecutive HCV RNA measurements  $\geq$  LLOQ (or 100 IU/mL for **Breakthrough**), either both during treatment or at the final treatment measurement and the next consecutive post-treatment measurement. A confirmed quantifiable post-treatment value is defined as any two consecutive post-treatment HCV RNA measurements  $\geq$  LLOQ.

**Breakthrough** = confirmed HCV RNA  $\geq$  100 IU/mL after HCV RNA < LLOQ during the Treatment Period; or confirmed increase from nadir in HCV RNA (two consecutive HCV RNA measurements > 1 log10 IU/mL above nadir) at any time point during the Treatment Period. A single breakthrough value ( $\geq$  100 IU/mL or > 1 log10 above nadir) followed by lost to follow-up also will be considered a breakthrough (i.e., will not require confirmation).

**EOT failure** = HCV RNA  $\geq$  LLOQ at end of treatment with at least 6 weeks of treatment, where the HCV RNA value must be collected on or after Study Drug Day 36 and study drug duration  $\geq$  36 days.

**On-treatment HCV virologic failure** = **Breakthrough** or **EOT failure**; if a subject meets both definitions of **Breakthrough** and **EOT failure**, he or she will be categorized as **Breakthrough** only.

**SVR4** = HCV RNA  $<$  LLOQ in the SVR4 window (4 weeks after the last actual dose of study drug) without any confirmed quantifiable ( $\geq$  LLOQ) post-treatment value before or during that SVR window.

**SVR12** = HCV RNA  $<$  LLOQ in the SVR12 window (12 weeks after the last actual dose of study drug) without any confirmed quantifiable ( $\geq$  LLOQ) post-treatment value before or during that SVR window.

**SVR24** = HCV RNA  $<$  LLOQ in the SVR24 window (24 weeks after the last actual dose of study drug) without any confirmed quantifiable ( $\geq$  LLOQ) post-treatment value before or during that SVR window.

**Relapse12** = confirmed HCV RNA  $\geq$  LLOQ between end of treatment and 12 weeks after last actual dose of study drug (up to and including the SVR12 assessment time point) for a subject with HCV RNA  $<$  LLOQ at Final Treatment Visit who completed treatment and has post-treatment HCV RNA data available, excluding reinfection as described below.

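### The only count of lost HIV suppression cannot include a rise first seen at end of treatment and repeated per protocol, nor any post-treatment rise

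*SAP*

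**What the plan says.** - **Protocol 5.4.1.2** sets the criterion for subjects on stable ART: HIV-1 RNA of at least 200 copies/mL "confirmed on 2 consecutive tests at least 2 weeks apart, in a subject compliant with their HIV ART therapy". HIV-1 RNA is followed in both the Treatment and Post-Treatment Periods.
- **Protocol Appendix C**, in the footnotes on HIV-1 RNA, allows the repeat as an unscheduled draw but says it "must be performed at least 2 weeks apart from the prior HIV-1 RNA result". Draws are scheduled at Weeks 2, 4, 8, 12 and, where applicable, 16, and then at Post-Treatment Weeks 4, 12 and 24.
- **Protocol 8.1.5.3** plans the summary "For the HCV/HIV co-infected subjects who were on stable HIV-1 ART at initiation of study drug": the number and percentage with two consecutive values of at least "200 copies/mL during the Treatment Period will be calculated". It states no spacing and no ART-compliance condition.
- **SAP 11.6** repeats that count and adds a limit on data source: "copies/mL during the Treatment Period will be calculated; only data from the central laboratory will be included in this analysis". The next sentence plans a listing of every subject with a value of 200 or more at any visit in the study.
- **SAP Table 4**, for HIV-1 RNA: "For all windows, data must be on or before Study Drug End Day 2".
- **SAP 10.1**, for HCV RNA, treats a quantifiable value as confirmed when the two measurements are "either both during treatment or at the final treatment measurement and the next consecutive post-treatment measurement".

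**The concern.** The protocol fixes a minimum gap between the two tests. The analysis fixes a closing date for both tests that is shorter than that gap when counted from the last on-treatment visit. The two rules together exclude a class of events by construction, whatever the data show.

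At stake is the only planned numeric summary of lost HIV suppression. A table could report no failures while a subject meets the protocol's own criterion on the basis of an end-of-treatment value and its repeat. The SAP already solved the same problem for HCV RNA by letting the next post-treatment value confirm the final on-treatment one, and it gives no reason for treating HIV-1 RNA differently.

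**Working it through.** The plan states no figure for this count, so there is none to reproduce. The check is day arithmetic on the nominal schedule.

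**Inputs**
- Last dose: Study Day 84 (12 weeks) or 112 (16 weeks).
- Cutoff for on-treatment HIV-1 RNA: last dose + 2 days (SAP Table 4).
- Earliest repeat under the protocol: first elevated value + 14 days (protocol 5.4.1.2 and Appendix C).
- Maximum number co-infected: 16 (protocol 5.1, SAP 4.2).

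**Rule.** A pair counts only if first-rise day + 14 ≤ last-dose day + 2, that is, if the first rise is no later than last-dose day − 12. This gives Day 72 for 12 weeks and Day 100 for 16 weeks.

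| Duration | First rise seen | Earliest repeat | Cutoff | Can count? |
|---|---|---|---|---|
| 12 weeks | Day 14, 28 or 56 | Day 28, 42 or 70 | Day 86 | yes |
| 12 weeks | Day 84 (EOT) | Day 98 = End Day 14 | Day 86 | no |
| 16 weeks | Day 14, 28, 56 or 84 | Day 28, 42, 70 or 98 | Day 114 | yes |
| 16 weeks | Day 112 (EOT) | Day 126 = End Day 14 | Day 114 | no |

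The Week 12 and Week 16 windows run to Days 98 and 126, so the earliest repeats would just fit them. The End Day 2 condition applies to all windows and overrides this.

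**Premature discontinuation.** Protocol 5.4.1 puts that visit between the day of the last dose and 2 days later. A first rise there has its earliest repeat at End Day 0 + 14 = 14 to 2 + 14 = 16, after the cutoff.

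**Post-treatment rises.** Values from Post-Treatment Weeks 4, 12 and 24 enter no count of confirmed rises.

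**Effect of one missed case.** One case out of n is 100/n percentage points. The denominator is the ART-treated subset, so n is at most 16: 100/16 = 6.25. The number on ART is not given. As assumed values, n = 10 gives 10 points and n = 5 gives 20.

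The SAP plans no interval for this count. For illustration, the 95% Wilson interval is (p + z²/2n ± z√[p(1−p)/n + z²/4n²]) / (1 + z²/n), with z = 1.96:
- 0/16: 0% (0.0 to 19.4)
- 1/16: 6.25% (1.1 to 28.3)

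**After the change.** An EOT rise could be confirmed by an unscheduled draw from End Day 14, or at Post-Treatment Week 4 (nominal End Day 28), and would then count.

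**The case against.** The other side has several good arguments.

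- **The SAP follows the protocol's statistics section.** This stands. Both the Treatment Period limit and the lack of a spacing rule are in protocol 8.1.5.3. A reader might infer that the SAP departed from the protocol on these points, but it did not. The mismatch is between 8.1.5.3 and 5.4.1.2.
- **Nothing is concealed.** This stands too. The SAP 11.6 listing covers any value of 200 or more at any visit. For South Korean subjects, a repeat of 500 or more can also enter the HIV resistance summary in SAP 10.8. But the listing mixes single and confirmed values and gives no confirmed number or percentage.
- **5.4.1.2 guides subject management and is not an endpoint, and it requires ART compliance.** This is fair. The count cannot simply be called the 5.4.1.2 rate unless compliance is addressed as well as spacing.
- **Other safety threshold counts are on-treatment only, and HCV confirmation concerns efficacy.** This is a reason to keep the on-treatment count. It does not explain why the final on-treatment value has no route to confirmation.
- **The exclusion is not absolute.** Correct. The SAP count has no spacing rule, so two on-treatment values closer than 2 weeks would count. So could an end-of-treatment sample drawn 12 or more days before the last dose.

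Two stronger readings are tempting. One is that the study would miss HIV loss of control caused by the study drugs. The documents do not name that as the cause of lost suppression: protocol 3.0 reports no clinically meaningful effect on the evaluated antiretrovirals, and 5.6.4.1.1 expects no significant interaction with allowed regimens. The other is that the central-laboratory limit discards local confirmatory tests. It would if such tests existed, but no text says they will occur; the protocol permits an unscheduled draw and does not mention local analysis.

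**Conclusion.** The point holds as a limited one. If the repeat is taken as the protocol requires, a first rise at the end-of-treatment or premature discontinuation visit, or any first rise fewer than 12 days before the last dose, cannot enter the count. Confirmed post-treatment rises are left out altogether. The reported number and percentage can be too low, by at least 6.25 percentage points per missed case.

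The exclusion itself rests only on the stated schedule and cutoffs. How often it would matter cannot be derived. If onset were uniform over treatment, the last visit interval would hold 4/12 = 33% of on-treatment failures in 12-week subjects and 4/16 = 25% in 16-week subjects, but nothing in the documents supports uniform onset, so these shares should not be quoted as findings. SAP 12.1 expects fewer co-infected subjects than planned. No primary or secondary efficacy conclusion depends on this. It is a cheap improvement to a safety summary.

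**What to change.** In SAP 11.6, with matching text in protocol 8.1.5.3:

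1. Keep the on-treatment count, but allow a final on-treatment value of 200 copies/mL or more to be confirmed by the next consecutive post-treatment value, as SAP 10.1 does for HCV RNA.
2. Add a separate row for confirmed rises whose first value is post-treatment. SAP Table 5 leaves Post-Treatment Week 24 out of the primary report, so a Week 12 rise confirmed at Week 24 would appear only in the final report. A rise first seen at Week 24 has no later scheduled draw.
3. Reconcile the count with 5.4.1.2 by stating whether the 2-week spacing and ART compliance apply and, if so, how compliance is judged. If the count is meant to differ from 5.4.1.2, say so in the table title.
4. Only if local HIV-1 RNA results are expected, state how they are used.

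The cost is wording and one table row, with no new scheduled samples. The reported rate may be slightly higher.

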## **12.0 Summary of Changes**

### **12.1 Summary of Changes Between the Latest Version of the Protocol and SAP**

1. Modified the definitions of the mITT populations to also exclude subjects who received incorrect duration of treatment due to incorrect classification of GT or treatment experience at enrollment.
2. Removed the analyses of demographics, baseline characteristics, study drug exposure and compliance for the mITT populations because it is expected that these populations will be very similar to the ITT population.
3. Replaced analyses by geographic region with analyses for the geographic region of China because analyses for the subset of subjects from China, rather than analyses by geographic region, are required by the regulatory agency. Certain analyses of subject disposition and SVR12 will be performed by geographic region.
4. Added additional analyses of categorical baseline characteristics for subjects with HCV/HIV co-infection at Screening to provide additional information for the HCV/HIV co-infected population.
5. Added analyses of SVR12 for the geographic region of China to sensitivity analysis to address regulatory requirements for China-specific analyses.
6. Added additional imputation approaches to the sensitivity analysis of the primary endpoint to align with the HCV ABT-493/ABT-530 program.
7. Removed the subgroup analysis of the primary endpoint for the mITT populations to align with the HCV ABT-493/ABT-530 program.
8. Added the additional efficacy analysis of the percentage of subjects with HCV virologic failure through PT Week 12 to align with the HCV ABT-493/ABT-530 program.
9. Removed several of the additional efficacy analyses to be performed on the HCV/HIV co-infected population because the number of HCV/HIV co-infected

subjects is anticipated to be lower than had been expected at the time the protocol was written.

10. Removed word "cumulative" from the analysis of subjects who have ever experienced an increase from baseline in the FSS total score of greater than or equal to 0.7 through each applicable timepoint to align with the HCV ABT-493/ABT-530 program.
11. Specified the assays used by the central laboratory for the HCV RNA and HIV-1 RNA samples and the HIV-1 resistance testing, along with the LLOD and LLOQ for the HCV RNA assay. This information was not known at the time of protocol development.
12. Removed several of the safety analyses to be performed on the HCV/HIV co-infected population because the number of HCV/HIV co-infected subjects is anticipated to be lower than had been expected at the time the protocol was written.
13. Added analysis of laboratory assessments of hepatotoxicity to align with the HCV ABT-493/ABT-530 program.
14. Added plots of mean change ( $\pm$  standard error) from baseline for ALT and bilirubin (total, direct, and indirect) to align with the HCV ABT-493/ABT-530 program.
15. Added shift tables for Child-Pugh score to align with the HCV ABT-493/ABT-530 program.
16. Added analyses of CD4+ T-cell count, CD8+ T-cell count, and lymphocytes for the HCV/HIV co-infected population to align with the HCV ABT-493/ABT-530 program.

